3.1.6 Prior and concomitant medication

Medications taken by any subject at any time during the study will be coded using the ATC classification system within the WHO Drug Dictionary.

Medications will be categorised for analysis according to their onset and end dates as follows:

- Prior medications:
 - end date \leq date of first dose of IP
- Concomitant medications during on-treatment period:
 - end date $>$ date of first dose of IP and start date \leq minimum (date of last dose of IP + 33 days, date of death, date of study withdrawal), or
 - end date ongoing and start date \leq minimum (date of last dose of IP + 33 days, date of death, date of study withdrawal)
- Concomitant medications during post-treatment period (for subjects still being followed up then):
 - start date $>$ date of last dose of IP + 33 days.

Essentially the above says that:

- Prior and concomitant medications are mutually exclusive.
- Concomitant medications on-treatment and post-treatment are also mutually exclusive (here, the word “concomitant” means concomitant with study procedures, irrespective of whether IP was still being taken). Specifically, a concomitant

medication which started on-treatment and ended post-treatment will only be considered on-treatment.

If the medication record has a completely missing onset date, the subject will be assumed to have been on the medication on the date of the first study procedure. If the medication record has a partially missing onset date (month/year or year only) which is the same as that for the end of IP treatment, it will be assumed to have started on-treatment. If the medication record has a partially missing onset date (month/year or year only) which is the same as that for the start of IP treatment, it will be assumed to have started before treatment.

If the medication record has a completely missing end date, the subject will be assumed to have been on the medication on the date of study completion or withdrawal. If the medication record has a partially missing end date (month/year or year only) which is the same as that for start of IP treatment, it will be assumed to have ended on-treatment. If the medication record has a partially missing end date (month/year or year only) which is the same as that for end of IP treatment, it will be assumed to have ended post-treatment.

In the above, note that for subjects entering the extension study, the study completion date will be the day of enrolment in the extension study.

3.1.7 Definition of subgroups

The following subgroups are defined for the purposes of efficacy subgroup analysis (indicated with a *), exposure-response analyses (indicated with a #) and/or demographic and baseline summaries:

- *Baseline eosinophils group: $<300/\mu\text{L}$, $\geq 300/\mu\text{L}$
- *Baseline eosinophils group: $<150/\mu\text{L}$, $150-<300/\mu\text{L}$, $300-<450/\mu\text{L}$, $\geq 450/\mu\text{L}$
- *Baseline eosinophils group: $<150/\mu\text{L}$, $\geq 150/\mu\text{L}$
- *Baseline clinic visit FENO group: $<25\text{ppb}$, $\geq 25\text{ppb}$
- *Baseline clinic visit FENO group: $<25\text{ppb}$, $25-<50\text{ppb}$, $\geq 50\text{ppb}$
- Baseline (Any) specific IgE status (FEIA): Any FEIA positive, All FEIA negative, Unknown FEIA
 - “Any FEIA positive” requires 1 or more specific IgE panels using fluorescent enzyme immunoassay (FEIA) to be positive. Provided that at least one IgE panel is positive, no further requirement is made for data on all 12 panels to be available.

- “All FEIA negative” requires all 12 specific IgE panels to be negative. If there are fewer than 12 panels with data available and none of these is positive, then IgE status is considered “Unknown FEIA”.
- Positive is defined as a value ≥ 0.35 kU/L.
- * Baseline perennial specific IgE status (FEIA): Any perennial FEIA positive, All perennial FEIA negative, Unknown perennial FEIA
 - “Any perennial FEIA positive” requires 1 or more specific IgE (FEIA) panels to be positive. Provided that at least one IgE panel is positive, no further requirement is made for data on all 8 panels to be available.
 - “All perennial FEIA negative” requires all 8 specific IgE panels to be negative. If there are fewer than 8 panels with data available and none of these is positive, then IgE status is considered “Unknown perennial FEIA”.
 - Positive is defined as a value ≥ 0.35 kU/L. The 8 panels include: American Cockroach, Cat Dander, D. farina, D. pteronyssinus, Dog Dander, German Cockroach, Mould Mix, Oriental Cockroach.
- Baseline seasonal specific IgE status (FEIA): Any seasonal FEIA positive, All seasonal FEIA negative, Unknown seasonal FEIA
 - “Any seasonal FEIA positive” requires 1 or more specific IgE (FEIA) panels to be positive. Provided that at least one IgE panel is positive, no further requirement is made for data on all 4 panels to be available.
 - “All seasonal FEIA negative” requires all 4 specific IgE panels to be negative. If there are fewer than 4 panels with data available and none of these is positive, then IgE status is considered “Unknown seasonal FEIA”.
 - Positive is defined as a value ≥ 0.35 kU/L. The 4 panels include: Grass Mix Pollen, Silver Birch Pollen, Weed Mix Pollen, Japanese Cedar.
- *ICS dose at study entry: medium, high (as defined in CSP Appendix F)
- *OCS at baseline: present, absent
 - OCS at baseline will be defined as OCS administered at baseline for disease under study.
- Age category used for stratification: adults (≥ 18) and adolescents (≥ 12 to < 18)
- *Age category: adults (≥ 65), adults (≥ 18 to < 65) and adolescents (≥ 12 to < 18)

- *Gender: Male, Female
- *Race: White, Black or African American, Asian, Other
- *Exacerbations in the year before study: ≤ 2 exacerbations, > 2 exacerbations
 - Note: no subjects are permitted to be randomised with a history of fewer than 2 exacerbations according to the eligibility criteria. However, the definition “ ≤ 2 ” is used for analysis purposes, to prevent exclusion of a subject from the primary analysis in the unlikely event of an important protocol deviation in this regard.
- *Baseline body mass index (BMI): < 18.5 kg/m², 18.5 - < 25.0 kg/m², 25.0 - < 30.0 kg/m², ≥ 30.0 kg/m²*Geographical region: Asia Pacific [incl. Japan, China, South Korea, Taiwan and Vietnam], North America [incl. Canada and USA], South America [incl. Argentina and Brazil], Central/Eastern Europe [incl. Russia and Ukraine], Western Europe plus Australia [incl. Austria, France, Germany, UK and Australia], Rest of World [incl. Israel, Saudi Arabia and South Africa]
- Country
- Baseline CRSwNP status: Yes, No
 - Chronic rhinosinusitis with nasal polyps at baseline will be defined by the presence of the following on the Respiratory Disease History eCRF page for a particular subject: Nasal polyps plus at least one of (Diagnosis of rhinitis; Diagnosis of chronic sinusitis).
- Nasal polyps status at study entry: Yes, No
 - Nasal polyps at baseline will be defined by the presence of nasal polyps on the Respiratory Disease History eCRF page for a particular subject.
- *Nasal polyps in the 2 years before randomisation status: Yes, No
 - Nasal polyps in the 2 years before randomisation will be defined by the presence of nasal polyps on the Respiratory Disease History eCRF page for a particular subject, with no associated stop date on the Medical History eCRF or an associated stop date less than, or equal to 24 months before randomisation.
- Chronic sinusitis status at study entry: Yes, No

- Chronic sinusitis at baseline will be defined by the diagnosis of chronic sinusitis on the Respiratory Disease History eCRF page for a particular subject.
- Rhinitis status at study entry: Yes, No
- Rhinitis at baseline will be defined by the diagnosis of rhinitis on the Respiratory Disease History eCRF page for a particular subject.
- *Biomarker quartiles
- The four, mutually exclusive, biomarker quartiles will be derived using the baseline FENO, eosinophil and total serum IgE data. This will ensure that the same quartiles will be used for all endpoints analysed.
- #Weight quartiles
- The four, mutually exclusive, weight quartiles will be derived using the baseline weights.
- #Drug concentration exposure quartiles
- The four, mutually exclusive, quartiles will be derived using the median trough steady state drug concentration data. The median trough steady state is calculated as the median of the observed drug concentration data at weeks 24, 36 and 52 for each individual subject.

3.1.8 Disposition

The following definitions will be used for time to event variables in Kaplan-Meier disposition plots:

Time to last dose of IP

Time to last dose of IP will be defined as follows:

$$\text{Time to last dose (days)} = [\text{Date of last dose of IP from eCRF} - \text{date of first dose of IP}] + 1.$$

Date of last dose of IP will be the date of last dose taken from the “Discontinuation of Investigational Product” eCRF page for all subjects; those who prematurely discontinue IP as well as those who complete IP dosing as per protocol.

Time to premature study withdrawal

Time to premature study withdrawal will be defined as follows:

Time to premature study withdrawal (days) = [study withdrawal date from eCRF – date of randomisation] + 1.

Study withdrawal date will be the completion or discontinuation date from the “Disposition” eCRF page, where any subject status other than “Completed” has been entered.

Subjects who did not prematurely withdraw from study will be censored at one of the following dates:

- Completion or discontinuation date from the “Disposition” eCRF page, where subject status of “Completed” has been entered.
- At primary DBL, ongoing subjects will be censored at their last contact date.

3.2 Derivation of efficacy variables

3.2.1 Primary endpoint

3.2.1.1 Annualised asthma exacerbation rate over 52 weeks

An asthma exacerbation (recorded on the exacerbation eCRF page) is defined in the CSP as a worsening of asthma that leads to any of the following:

- A temporary bolus/burst of systemic corticosteroids (or a temporary increase in stable OCS background dose) for at least 3 consecutive days to treat symptoms of asthma worsening; a single depo-injectable dose of corticosteroids will be considered equivalent to a 3-day bolus/burst of systemic corticosteroids
- An emergency room or urgent care visit (defined as evaluation and treatment for <24 hours in an ER or UC centre) due to asthma that required systemic corticosteroids (as per above)
- An inpatient hospitalisation (defined as admission to an inpatient facility and/or evaluation and treatment in a healthcare facility for ≥ 24 hours) due to asthma.

The start of an exacerbation is defined in the CSP as the start date of systemic corticosteroids, ER or UC visits requiring systemic corticosteroids, or hospital admissions due to asthma, whichever occurs earlier. The end date is defined in the CSP as the last day of systemic corticosteroids or ER/UC/hospital discharge, whichever occurs later.

Two or more exacerbations with the same start date and end date will be counted as one exacerbation for the purposes of calculating the number and duration of exacerbations for a subject. In the case that one or more exacerbations are recorded as starting or ending during another exacerbation, these will be counted as one exacerbation, using the earliest exacerbation start date and the latest exacerbation stop date to calculate duration.

Additional systemic corticosteroid treatments, ER or UC visits requiring use of systemic corticosteroids, or inpatient hospitalisation due to asthma occurring during an exacerbation will not be regarded as a new exacerbation. To be counted as a new exacerbation it must be preceded by at least 7 days in which neither criterion is fulfilled. If the end date of the first exacerbation and the start date of the second exacerbation are less than 7 days apart, then these will be counted as one exacerbation.

For on-treatment analyses the time at risk during which an exacerbation will be included is defined in [Section 2.1.5](#).

For planned treatment analyses, the time at risk will be defined as follows:

If the subject attended Visit 17/EOT Week 52 (expected to be the majority of subjects), then:

$$\text{Time at risk (days)} = [\text{earliest (Date of Visit 17; date of last exacerbation assessment status from the eCRF)} - \text{date of randomisation}] + 1$$

Otherwise, if no Visit 17/EOT Week 52 is available for a subject:

$$\text{Time at risk (days)} = [\text{earliest (randomisation date} + 364 \text{ days} + 5 \text{ days; date of last exacerbation assessment during planned treatment)} - \text{date of randomisation}] + 1,$$

where:

Date of last exacerbation assessment during planned treatment = Latest of:

1. *the date of last assessment of exacerbation status from the eCRF.*
2. *the date of death*

The number of days the subject experiences a protocol defined exacerbation, including the subsequent 7 days (when a further exacerbation would not be considered as a second exacerbation), will be subtracted from the time at risk defined above for the primary analysis. For example, if a subject has a single exacerbation which lasts 4 days then $7 + 4 = 11$ days will be subtracted from the time at risk.

It should be noted that the date of last assessment of exacerbation status from the eCRF might be later than the last available visit during the planned treatment period, in the case that the subject remained in the study with incomplete follow-up options after early discontinuation of IP.

For the primary analysis (planned treatment), exacerbations that occur after a subject has discontinued IP but before the end of the time at risk will still be accounted when deriving the total number of exacerbations. Likewise, the time at risk will reflect the time at risk regardless of whether the subject is still on IP or not.

Any exacerbations that starts within the time at risk but ends after this time point will be included in analyses with the end date adjusted to be no later than the time at risk. Any exacerbation that starts after this time will not be included in analyses.

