The study is designed to dose subjects at Q4W with the last dose given at week 48, EOT visit at week 52, and a 12-week follow-up period.

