7.1.1 Procedures for discontinuation of study treatment

Subjects are free to discontinue IP or withdraw from the study at any time without prejudice to further treatment. Discontinuing study treatment is not the same as study withdrawal. Procedures to follow for study withdrawal are detailed below in section 7.3. If the subject decides to withdraw consent, then the reason for this must be recorded separately in the eCRF.

A subject that decides to discontinue IP should always be asked about the reason(s) and the presence of any adverse events. The reason for discontinuing treatment and the date of last IP administration should be recorded in the eCRF. Subjects permanently discontinuing IP administration should be given locally available standard of care therapy, at the discretion of the Investigator. However, treatment with marketed or investigational biologics is not allowed until week 64 even if the subject has discontinued IP. Interaction studies between tezepelumab and other biologics indicated for the treatment of asthma have not been conducted. For additional information regarding pharmacokinetic and pharmacodynamic effects of tezepelumab reference should be made to the investigator brochure.

All subjects who prematurely discontinue IP should return to the study center and complete the procedures described for the premature IP Discontinuation visit (IPD) at 4 weeks (+/-5 days) post last IP administration. Subjects who discontinue treatment should be encouraged to return for all regularly scheduled visits for safety and efficacy assessments.

At the IPD visit the subject will be given three options as to how they will be followed as follows:

1. The subject should be encouraged to return for all regular clinic visits and perform all scheduled assessments until he/she completes a total of 52 weeks treatment period.
2. The subject will be offered follow-up on a monthly basis via telephone calls while continuing diary and ePEF completion (no further procedures will be performed), until the subject completes 52 weeks in the study. In addition to the PRO assessments that are performed at home, the subject may also complete the other clinic specified PRO assessments (as defined in the SoA) at home as well. The subject should return for a follow-up visit 16 weeks (+/- 5 days) (refer to SoA, V19 – Week 64) post last IP administration and for the EOT visit at Week 52 (+/-5 days).

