3. If the subject cannot or does not wish to comply with any of the options above, (or any component of them such as only telephone based visits without completion of the diary and ePEF), they will complete a follow-up visit at 16 weeks (+/-5 days) (refer to SoA, Visit 19 – week 64) post last IP administration. After this visit the Investigator

will only contact the subject at 52 weeks post-randomization. No other study assessments will be performed prior to this contact.

If the last IP administration was after week 36 for options 1 or 2, the subject will return to the clinic for an EOT visit at Week 52 (+/- 5 days), and for option 3, the investigator will contact the subject at 52 weeks post randomization. The subject for options 1, 2 and 3 will then return for a follow-up visit 16 weeks (+/- 5 days) post last IP administration (refer to SoA, V19 – Week 64).

The EOT visit will be completed immediately in the case of subsequent early withdrawal from option 1 or 2. Subjects who do not wish to have any follow-up contacts will be discontinued from the study. All discontinued subjects must return the diary and ePEF devices at the EOT visit.

If the subject chooses option 1, all assessments will be completed as per the SoA as indicated in Section 1.1. If the subject chooses 2 or 3, the key information to be collected during the telephone calls are AEs/SAEs, changes in concomitant medication, health care utilization, and asthma exacerbation information.

Subjects who initially choose options 1 or 2 and subsequently cannot or do not wish to comply with the requirements of their option can continue with a less intensive option (i.e. subject initially choosing option 1 can continue with options 2 or 3, subjects initially choosing option 2 can continue with option 3).

If a subject discontinues IP due to a study specific discontinuation criterion, this should always be recorded as 'Development of study specific discontinuation criteria' on the Discontinuation of Investigational Product form in the eCRF.

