9.4.3 Efficacy analysis

9.4.3.1 Analysis of the primary efficacy endpoint

The primary analysis of the primary efficacy endpoint (AAER over 52 weeks) will quantify the effect of the initially randomized treatment, regardless of the treatments that subjects actually received, or whether the subjects received other controller therapy/rescue medications post IP discontinuation. This analysis will therefore include all available data after treatment discontinuation. Subjects will be encouraged to continue to undergo applicable study related visits/procedures for the full 52-week period even after premature discontinuation of IP. Consequently, subjects lost to follow-up and subjects who withdraw their consent will be the only source of missing information for the primary analysis. Missing data from study discontinuation will be modelled based on what was observed during the study using direct likelihood approaches, which is a valid approach under the assumption that data are missing at random (MAR).

AAER in the tezepelumab group will be compared to that seen in the placebo group using a negative binomial model. This model will be used to perform the statistical test specified in Section 9.1, and to estimate the treatment effect and both its 99% and 95% confidence intervals. The response variable in the model will be the number of asthma exacerbations experienced by a subject over the 52-week study period (or shorter duration if not followed up for the full 52 weeks). Treatment, region, age (adolescents or adults) and history of exacerbations (2 or >2 in previous 12 months) will be included as factors in this model. The logarithm of the time at risk for exacerbation in the study will be used as an offset variable in the model, to adjust for subjects having different follow-up times during which the events occur. Time during an exacerbation and the 7 days following an exacerbation in which a new exacerbation cannot occur, will not be included in the calculation of time at risk for exacerbation.

Descriptive summaries of the asthma exacerbations will also be presented.

Annualized rates for the individual exacerbation criteria (emergency room or urgent care visits due to asthma that required systemic corticosteroids, hospitalization due to asthma, or use of

systemic corticosteroids) will be summarized descriptively and analyzed using a similar model as for the primary endpoint.

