3.1.4 Study periods

The following study periods are defined for analysis purposes:

- Screening/run-in period: starting on the date of the first study procedure and ending one day prior to randomisation (for randomised subjects) or on the date of the last study procedure (for screening failures). If any subject is re-screened, the latest available screening will be used for this purpose.
- Planned treatment period (on-treatment and off-treatment): starting on the date of randomisation (efficacy) / date of first dose of IP (safety) and ending on the date of the Week 52 visit or earlier study withdrawal date (for subjects not followed up until Week 52).
- On-treatment period: starting and ending on the start and end dates defined in [Section 2.1.5](#) for efficacy and safety analyses, respectively.
- Post-treatment period/Follow-up period: starting one day after the end date of the on-treatment period defined in [Section 2.1.5](#) for efficacy and safety analyses, respectively, and ending on the study completion or withdrawal date. Note: for subjects entering the extension study, the study completion date will be the day of enrolment in the extension study.
- On-study period (planned treatment and follow-up): starting on the date of randomisation (efficacy) / date of first dose of IP (safety) and ending on the study completion or withdrawal date. Note: for subjects entering the extension study, the study completion date will be the day of enrolment in the extension study. For analysis performed at primary database lock, the on-study period is understood to include all data recorded up until the date of the data cut-off for the primary

database lock (which includes all follow-up data available at the time of the data cut-off).

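### The primary time at risk is capped at Week 52 plus 5 days only for subjects without Visit 17; an out-of-window Visit 17 can lengthen it past 52 weeks and, depending on coding, an early EOT visit can cut it short

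*SAP*

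**What the plan says.** The primary endpoint is the exacerbation rate over 52 weeks. Protocol 9.4.3.1 gives the model's response as "number of asthma exacerbations experienced by a subject over the 52-week study period (or shorter duration if not followed up for the full 52 weeks", and SAP 4.2.4.1 is to the same effect. Both allow a shorter period and neither allows a longer one.

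SAP 3.2.1.1 then has two branches for the end of time at risk:

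- **Visit 17 attended** (expected for most subjects): "earliest (Date of Visit 17; date of last exacerbation assessment status from the eCRF". No day limit is given.
- **No Visit 17:** the earlier of randomisation + 364 + 5 days and the last exacerbation assessment during planned treatment, which is the later of the last eCRF exacerbation-status date and death.

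Events that start before the end of time at risk count whether or not the subject is on drug. Events that start after it are excluded. SAP 3.1.4 has the planned treatment period "ending on the date of the Week 52 visit or earlier study withdrawal date", so it supplies no cap.

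The protocol sets the last dose at Week 48 (4.3) and has subjects on follow-up option 2 return "for the EOT visit at Week 52 (+/-5 days" (7.1.1). On leaving follow-up early, 7.1.1 says: "The EOT visit will be completed immediately in the case of subsequent early withdrawal from option 1 or 2". The same section lets a subject step down to option 3, where a contact at 52 weeks collects exacerbation information.

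**The concern.** The cap is missing from the branch that covers most subjects. The second term in that branch can only shorten the period, so it does not limit a late visit. SAP 3.1.5 itself allows for visits well before or after schedule. From Day 379, SAP Table 1 labels an assessment Follow-up Week 58, while the primary endpoint would still count exacerbations up to that visit.

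Three things follow.

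- **Primary and Level 2 tests.** Time after Week 52 is largely off treatment. The log offset corrects for length of follow-up, not for a different event rate once drug is stopped.
- **Other exacerbation endpoints (SAP 3.2.4.1).** Time to first exacerbation is censored using the same end date. The exacerbation-free endpoint requires more than 359 days but sets no maximum and has no offset, so a subject event-free for 52 weeks can be scored a failure because of a later event.
- **Early EOT.** If that visit is recorded as Visit 17, the rule stops time at risk there and discards exacerbations reported at the 52-week contact. SAP 4.2.4.1 says all available data to the end of planned treatment are used under a treatment policy strategy.

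**Working it through.** **Where the two branches differ.** A Visit 17 at the latest in-window date falls on randomisation + 364 + 5 = randomisation + 369 days, which is the other branch's cap. A Week 48 dose given on schedule is at randomisation + 336, and SAP 2.1.5 ends on-treatment 33 days later, again at randomisation + 369. So the branches diverge only for out-of-window visits, and a late visit then adds off-treatment time.

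**Inputs (SAP 1.3).** Placebo rate 0.9 per year, rate ratio 0.5 (tezepelumab 0.45), shape 2.4, 530 per arm, 10% uniform dropout (mean follow-up t ≈ 0.95 year), 2-sided 1%. For eosinophils <300/µL: 265 per arm, placebo rate 0.6, 2-sided 5%.

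**The plan's own figures.** Variance of the log rate ratio = [(1/t)(1/r0 + 1/r1) + 2k]/n.

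- Primary: [(1/0.95)(1.111 + 2.222) + 4.8]/530 = 0.01568, SE 0.1252. Then 0.693/0.1252 − 2.576 = 2.96, power 99.8% (stated: at least 99%).
- Subgroup: [(1/0.95)(1.667 + 3.333) + 4.8]/265 = 0.03797, SE 0.1949. Then 0.693/0.1949 − 1.960 = 1.60, power 94.5% (stated: 94%).
- Smallest significant reduction: about 26.5% (stated: 27%).

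These reproduce and do not depend on the Visit 17 rule.

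**Late visits, worst case.** Assume a fraction f of subjects is d weeks late and the tezepelumab rate returns fully to 0.9 after Week 52. Counting the delay from Week 52, not from the cap, slightly overstates the effect.

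Ratio = (0.45 × 52 + f·d × 0.9) / [(52 + f·d) × 0.9]

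| f | d (weeks) | Ratio | Primary power | Subgroup power |
|---|---|---|---|---|
| 10% | 4 | 23.76/47.16 = 0.504 | 99.8% | 94.1% |
| 20% | 8 | 24.84/48.24 = 0.515 | 99.7% | 92.8% |
| 50% | 8 | 27.00/50.40 = 0.536 | 99.3% | 90.0% |
| 100% | 12 | 34.20/57.60 = 0.594 | 95.4% | 78.6% |

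The last two rows are stress tests, not expectations.

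**Exacerbation-free probability for a subject 8 weeks late.** P = (1 + 2.4m)^(−1/2.4), where m is the expected number of events.

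- Placebo: m = 0.9 gives 0.619; m = 0.9 × 60/52 = 1.038 gives 0.594.
- Tezepelumab, full loss of effect: m = 0.45 gives 0.737; m = 0.45 + 0.9 × 8/52 = 0.588 gives 0.693. If the on-drug rate persisted, m = 0.519 gives 0.714.

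For such a subject the difference between arms goes from 0.737 − 0.619 = 0.118 to 0.693 − 0.594 = 0.099. With 20% of subjects that late, the trial-level difference falls by 0.2 × 0.019 ≈ 0.004.

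**Early EOT, conditional on coding as Visit 17.** Suppose a share e of subjects each loses half a year of off-drug follow-up at the placebo rate. With y = 0.5e, the full-follow-up ratio is [(1 − y) × 0.45 + y × 0.9]/0.9. For e = 5% it is 0.513 and for e = 10% it is 0.525, while the truncated analysis would show 0.50. This error favours tezepelumab; the late-visit error works against it.

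**The case against.** The strongest reply is that this hardly matters. A compliant Visit 17 stops at the same day as the cap, the offset handles length of follow-up, and SAP 3.1.4 also ends the period on the visit date, so the SAP is internally consistent. That stands as a limit on size. It does not reconcile the formula with an endpoint of 52 weeks or shorter.

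Full loss of effect is also too severe. Protocol 5.3 equates 16 weeks with 5 half-lives, so one half-life is about 3.2 weeks and 2^(−4/3.2) = 42% of the Week 52 trough remains 4 weeks later. With linear PK, 70 mg Q4W gives about one third of the 210 mg exposure, and it still reduced the rate by 61% (protocol 2.2). This stands: the ratios above are upper bounds.

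A reader might infer that COVID-19 makes late visits common. The documents do not support that. Protocol Appendix I replaces on-site visits, including EOT, with home, alternate-site or remote ones, and SAP Appendix 8.4 summarises missed or changed-format visits, not delayed ones.

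A reader might also take the early-EOT loss as certain. It is not. The SAP's label is Visit 17/EOT Week 52, so a subject with only an early EOT could be treated as having none, and 3.2.1.1 foresees a status date later than the last visit. The SAP does not settle the point.

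The existing additional analyses do not cure the rule. The on-treatment analysis (SAP 4.2.4.3) answers a different question. The COVID-19 analysis stops at 10 March 2020 but keeps the same Visit 17 rule. The SAP's amendment history records removal of a sentence about using Visit 17 however late; the current formula still sets no limit.

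**Conclusion.** The concern holds as a gap in the endpoint definition. The attended-Visit-17 branch has no day limit, and this conflicts with a period of 52 weeks or shorter. It affects out-of-window visits only, not every attendee.

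For late visits the worst-case shift in the ratio is about 0.004 to 0.015 in the moderate scenarios, against tezepelumab, and primary power stays at 95% or more in every late-visit scenario tried. For a tezepelumab subject 8 weeks late, the exacerbation-free probability falls from 0.74 to about 0.69. The early-EOT part is conditional on how that visit is recorded and needs a stated rule. All of these sizes rest on assumed shares and delays and on full loss of effect off drug.

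A reader might infer that the primary result is at risk. The figures do not support that; the case for changing the rule is that the endpoint should measure what it is said to measure.

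**What to change.** In SAP 3.2.1.1, apply the attended-Visit-17 branch only when the Visit 17 date lies within Week 52 ±5 days. Otherwise, for all subjects, use the earlier of randomisation + 364 + 5 days and the date of last exacerbation assessment during planned treatment, as already defined there. This caps late visits and stops an out-of-window early EOT visit from overriding a later exacerbation-status date.

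Use the same exacerbation end date in SAP 3.2.4.1 (time to first exacerbation and exacerbation-free) and in Appendix 8.4, with 10 March 2020 as the further cap there.

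Leave the planned treatment period in SAP 3.1.4 unchanged for visit-based endpoints. SAP 3.1.5 selects records in that period before assigning visit windows, and the Week 52 window is Days 351–378. Ending the period at randomisation + 369 (Day 370) would lose FEV1, AQLQ(S)+12 and ACQ-6 data from a Visit 17 on Days 371–378.

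The cost is one revised rule, two cross-references and a programming change before unblinding. The downside is that a few post-Week-52 events and person-days are no longer counted.
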